5.3.2. Infections and infestations

Infections and infestations refer to adverse events with SOC of infections and infestations. A summary of number of subjects with 1 or more toxicity Grade 3 or 4 treatment-emergent infections and infestations by MedDRA preferred term and relationship to treatment will be provided. Additional summary analyses may include by onset time (i.e., ≤ 6 months vs. $6 \leq 12$ months vs. $12 \leq 24$ months vs. ≥ 24 months) and/or exposure-adjusted incidence rate of infections/infestations.

32

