2.11.2. Linking of Treatment Emergent Adverse Events

All event records of the same preferred term from the same subject are to be linked by the onset date and the end date. If an event is followed by another event of the same preferred term with an onset date (or date/time) the same as or 1 day (or 1 minute if applicable) after the end date (or date/time) of the previous record and any features of the adverse event (i.e.: toxicity grades/seriousness/action taken) are different between these two records, these 2 records should be linked together and considered as 1 event, the maximal toxicity grade of the 2 records would be used for the analysis.

^a Includes mild (total bilirubin \leq ULN and AST > ULN or ULN < total bilirubin \leq 1.5 \times ULN), moderate (1.5 \times ULN < total bilirubin \leq 3 \times ULN), severe (total bilirubin > 3 \times ULN).

b. High risk is defined as positive for any of del17p, t(14:16) or t(4:14) by FISH/Karyotype.

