5.1. Adverse Events

All adverse events whether serious or non-serious, will be reported from the time a signed and dated informed consent form (ICF) is obtained until 30 days after the last dose of study treatment, until the subject withdraws consent for study participation, or until the subject starts subsequent antimyeloma therapy, whichever occurs first. AEs will be recorded in standard medical terminology and graded according to the National Cancer Institute Common Terminology Criteria for Adverse Events (NCI-CTCAE), Version 4.03. For AE reporting, the verbatim term used in the CRF by investigators to identify adverse events will be coded using the latest version of Medical Dictionary for Regulatory Activities (MedDRA) coding dictionary.

Unless otherwise specified, at each level (e.g., system organ class and/or preferred term) of subject summarization in reporting the incidence of the AE, a subject is counted once if one or more events were recorded. For summarizing new onset events, all event records of the same preferred term from the same subject are to be linked by the onset date and the end date. If an event is followed by another event of the same preferred term with an onset date (or date/time) the same as or 1 day (or 1 minute if applicable) after the end date (or date/time) of the previous record and any features of the adverse event (i.e.: toxicity grades/seriousness/action taken) are different between these two records, these 2 records should be linked together and considered as one event. A Grade 5 event will be linked to previous event of the same preferred term if the onset date of grade 5 record is the same or one day after the end date of previous record.

All summaries of AEs will be based on treatment-emergent adverse events (TEAEs), which are defined as any AE that occurs after start of the first study treatment through 30 days after the last study treatment; or the day prior to start of subsequent antimyeloma therapy, whichever is earlier; or any AE that is considered drug-related (very likely, probably, or possibly related) regardless of the start date of the event; or any AE that is present at baseline but worsens in toxicity grade or is subsequently considered drug-related by the investigator.

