5.1.3. Toxicity Grade 3 or 4 TEAEs

- Incidence of toxicity Grade 3 or 4 TEAEs, by MedDRA SOC and preferred term
- List of subjects with any toxicity Grade 3 or 4 TEAEs
- Most commonly reported (>5%) Grade 3 or 4 TEAE by MedDRA SOC and preferred term

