5.1.4. Study Treatment-Related TEAEs

- Incidence of TEAEs considered by the investigator to be related to study treatment, by MedDRA SOC, preferred term and relationship to study treatment
- Incidence of TEAEs with toxicity Grade 3 or 4 considered by the investigator to be related to study treatment, by MedDRA SOC and preferred term and relationship to study treatment

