5.3.1. Infusion-Related Reactions (IRR)

Subjects with any IRR associated with daratumumab administration will be summarized by MedDRA system-organ class and preferred term. The summaries will be presented by all grades, Grade 3, 4, and 5. In addition, the total number of subjects with IRR in more than 1 infusion will be reported. Additionally, the timing of IRR associated with daratumumab administration will be evaluated through a summary of IRR by event onset time.

A listing of subjects with Grade 3 or higher treatment-emergent infusion-related reactions associate with daratumumab administration will be provided. In addition, subjects with treatment-emergent infusion-related reactions results in discontinuation of daratumumab will be listed.

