4. ADDITIONAL TIME TO EVENT ANALYSES

In case of different exposure times, time adjustment for AE is necessary. Hazard Ratio and Kaplan-Meier curves will be conducted including number of patients at risk for the following safety endpoints:

- Any TEAE
- Any Serious TEAE
- Any TEAE leading to death
- Any Grade 3 or 4 TEAE
- Any Grade 3 or higher TEAE
- Any TEAE leading to treatment discontinuation

Detailed description by preferred term:

- TEAEs by preferred term with prevalence>=10%/
- Grade 3 or 4 TEAEs preferred term with prevalence>=5%
- Grade 3 or higher TEAEs by preferred term prevalence>=5%
- Serious TEAEs preferred term with prevalence>=2%
- TEAEs leading to treatment discontinuation preferred term with prevalence>=1%
- TEAE leading to death preferred term without prevalence cut-off

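### The severe-event tables, above all the infection table in SAP 5.3.2, stop at Grade 4, so a subject whose only severe infection was fatal is not counted in them

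*SAP*

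**What the plan says.** Three sets of SAP provisions bear on this.

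**Linking.** Section 2.11.2 joins contiguous records of one preferred term in one subject when a feature such as grade differs, and says "the maximal toxicity grade of the 2 records would be used for the analysis". Section 5.1 repeats the linking rule and adds a fatal case: "A Grade 5 event will be linked to previous event of the same preferred term", provided the Grade 5 onset is on the day the previous record ends or the day after. Section 5.1 introduces linking with a purpose: "For summarizing new onset events, all event records of the same preferred term from the same subject are to be linked". Section 2.11.2 states no such limit.

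**Severe-event tables.** Section 5.1.3 plans "Incidence of toxicity Grade 3 or 4 TEAEs, by MedDRA SOC and preferred term". The second bullet of 5.1.4 plans "Incidence of TEAEs with toxicity Grade 3 or 4 considered by the investigator to be related to study treatment". Section 5.3.2 plans "A summary of number of subjects with 1 or more toxicity Grade 3 or 4 treatment-emergent infections and infestations"; its other infection summaries (by onset time, exposure-adjusted) are optional. Sections 5.1.6, 5.1.7 and 5.3.2.1 to 5.3.4 also split at Grade 3 or 4, but beside an all-grades column.

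**Where Grade 5 is kept.** For infusion-related reactions (5.3.1): "The summaries will be presented by all grades, Grade 3, 4, and 5". Attachment 1, section 4, lists "Any Grade 3 or higher TEAE" as a separate line from Grade 3 or 4.

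**The concern.** Read literally, Grade 3 or 4 excludes Grade 5. It cannot be taken as loose wording for Grade 3 or higher, because Attachment 1 lists the two side by side and 5.3.1 names Grade 5 explicitly. The severe-event tables therefore omit the worst outcome of the events they describe.

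Infection is where this matters most. Protocol 16.1 names infection as a potential risk arising from daratumumab's mode of action, and 5.3.2 gives it a single committed table with neither an all-grades nor a Grade 5 column. In such a table, an infection that worsens to death can lower an arm's count. A reader using it to compare severe infection between arms would see too low a rate in both, and the shortfall would be larger in the arm with more subjects whose only severe infection was fatal.

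**Working it through.** The plan states no figure to reproduce. The check applies the SAP's wording to simple record patterns, asks which planned tables could supply the missing rate, and then sizes the gap under stated assumptions.

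**1. Which patterns are counted.** Records share one preferred term. Linking requires a start on the day the previous record ends or the day after, with a different grade; the linked event takes the maximum grade.

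| Pattern | Grade 3 or 4, unlinked | Grade 3 or 4, linked | Grade 3 or higher, linked |
|---|---|---|---|
| Grade 4 ends day 14, Grade 5 starts day 15 | counted | not counted | counted |
| Grade 3 ends day 14, Grade 5 on day 14 | counted | not counted | counted |
| Grade 4 ends day 14, Grade 5 starts day 17 | counted | counted | counted |
| Single Grade 5 record | not counted | not counted | counted |
| Grade 3 running into Grade 4 | counted | counted | counted |
| Grade 2 running into Grade 3 | counted | counted | counted |

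The stand-alone Grade 5 record is missed on either reading. The two contiguous patterns are missed only if tables use linked records. A subject with another Grade 3 or 4 infection stays in the any-infection count; the loss is then confined to the preferred-term row.

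**2. Whether another planned table gives the Grade 3-or-higher infection rate by arm.**

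| Source | Contains fatal infections? | Why it is not that rate |
|---|---|---|
| 5.1.1 overview by maximum grade 1 to 5 | yes | all TEAEs together, not infections |
| 5.1.2 all TEAEs by SOC and preferred term | yes | includes Grades 1 and 2 |
| 5.1.5 SAEs by SOC and preferred term | yes | seriousness is not grade |
| 5.2.1 deaths due to TEAEs | yes | fatal events only |
| Attachment 1, section 4 | yes | exploratory; any TEAE, or by preferred term with a 5% cut-off for Grade 3 or higher |

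Adding the deaths in 5.2.1 to the count in 5.3.2 does not work either: a subject with a fatal infection and a separate Grade 3 or 4 infection would be counted twice.

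**3. Size, by assumption.** Let s be the true proportion with a Grade 3-or-higher infection and f the proportion whose only such infection is left out because it was fatal. Then the table shows s − f, the relative understatement is f/s, and the number missing is 365 × f, using the 365 planned per arm (SAP 1.1). Both s and f are assumed.

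| f | Missing per arm | f/s at s = 15% | at 25% | at 35% |
|---|---|---|---|---|
| 1% | 365 × 0.01 ≈ 4 | 6.7% | 4.0% | 2.9% |
| 2% | 365 × 0.02 ≈ 7 | 13.3% | 8.0% | 5.7% |
| 3% | 365 × 0.03 ≈ 11 | 20.0% | 12.0% | 8.6% |
| 5% | 365 × 0.05 ≈ 18 | 33.3% | 20.0% | 14.3% |

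**4. Effect on the comparison.** With arms 1 and 2, the displayed difference is (s1 − f1) − (s2 − f2) = (s1 − s2) − (f1 − f2). The distortion equals the between-arm difference in f.

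**The case against.** The strongest reply is that this is largely a matter of presentation. Much of it stands.

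- **Fatal events are visible elsewhere.** Besides the tables in step 2 of the working, Attachment 1 plans analyses of TEAEs leading to death by preferred term without a prevalence cut-off. An excess of fatal infections in one arm would show directly in 5.2.1. A reader might infer that fatal infections disappear from the safety report; the documents do not support that.
- **Linking may not govern these tables.** Section 5.1 ties linking to new-onset summaries and counts a subject once if any event was recorded. On that reading a recorded Grade 4 pneumonia still counts when a Grade 5 record follows. Since 2.11.2 applies the maximal grade without that limit, the SAP is ambiguous, and linking cannot be asserted as the settled cause. The stand-alone Grade 5 omission does not depend on it.
- **Several tables are less affected.** Opportunistic infections, cytopenia and hemorrhage have all-grades columns, and 5.1.2 and the first bullet of 5.1.4 are all-grade counterparts of the two general severe tables.
- **Grade and outcome are separate.** Protocol 12.3.1 records death as an outcome, and 5.2.1 accepts either a fatal outcome or Grade 5. A fatal event graded 3 or 4 would remain in the table.
- **Layouts may be settled elsewhere.** SAP 5.3 defers some detail to the data presentation specification, which is not among the documents. Section 5.1 also says in general terms that TEAEs will be summarized by toxicity grade, but the specific tables it then lists include no Grade 3-or-higher table by SOC.

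None of this supplies the missing infection rate.

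**Conclusion.** The point holds as a reporting gap. As specified, 5.1.3, the second bullet of 5.1.4 and 5.3.2 omit stand-alone Grade 5 events, and may also omit severe events that run directly into a Grade 5 record. The consequence is sharpest for infection, where the one committed table cannot show the full severe rate by arm.

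The direction of the understatement follows from the wording; the size does not, because the documents give no adverse event rates. The range of about 4 to 18 subjects per arm, or roughly 3% to 33% in relative terms, rests wholly on the assumed f of 1% to 5% and s of 15% to 35%.

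A reader might go further and infer that the table would reverse the comparison. For example, with 30% true in both arms and fatal-only rates of 4% and 2%, it would read 26% against 28%, favouring the arm with more deaths. That needs assumed rates, no other Grade 3 or 4 infection in any of those fatal cases, and a fatal-only excess larger than the overall excess in the same arm. Nothing in the documents shows this will occur. The SAP plans no hypothesis test on these incidence tables, and the PFS analysis, its alpha and its power are unaffected.

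**What to change.** In SAP 5.3.2, 5.1.3 and the second bullet of 5.1.4, tabulate Grade 3 or higher by arm with Grade 5 in its own column, following 5.3.1. Keep a Grade 3 or 4 column if comparability with other reports is wanted. Add the same columns to the Grade 3 or 4 splits in 5.1.6, 5.1.7, 5.2.3 and 5.3.2.1 to 5.3.4. State in 2.11.2 and 5.1, in the same terms, whether incidence tables use linked or unlinked records.

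Counting Grade 3 or 4 before applying the Grade 5 link would not be enough, because it leaves out stand-alone Grade 5 records.

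The cost is revised table shells and a grade flag in the programming, with no new data. Reported severe-event percentages will be slightly higher. The final CSR analysis updates safety (Protocol 3.1 and 9.1.8), so the change would still be useful there if these layouts are reused.

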5.3.2.1. Opportunistic Infections

Opportunistic Infections to adverse events with PT terms which would be defined on the DPS. The summaries will be presented by all grades and Grade 3 or 4 for each treatment group.

5.3.3. Cytopenia

Cytopenia includes Neutropenia events, Thrombocytopenia events, Anaemia and Lymphopenia. The four types of Cytopenia to adverse events with PT terms which would be defined on the DPS. The summaries will be presented by all grades and Grade 3 or 4 for each treatment group.

5.3.4. Hemorrhage

Hemorrhage defined by Standardized MedDRA Queries (SMQ) with the first subcategory SMQ of hemorrhage terms (exclude laboratory terms). The summaries will be presented by all grades and Grade 3 or 4 for each treatment group.

5.3.5. Second Primary Malignancies

A listing of subjects who reported second primary malignancies during the study will be provided. This listing will include diagnosis, study day of diagnosis, recurrence of a prior existing malignancy (yes, no) and pathology diagnosis (biopsy, aspirate etc.) etc. information whenever a second primary malignancy is observed. In addition, cumulative study treatment exposure, the treatment for second primary malignancy and the outcome information will also be presented in the listing.

5.4. Clinical Laboratory Tests

The evaluation of clinical laboratory tests will focus on the following selected laboratory analytes:

Hematology panel:

- hemoglobin
- platelet count
- white blood cell (WBC) count with absolute neutrophils and lymphocytes

Blood chemistry panel:

- alkaline phosphatase
- creatinine
- uric acid
- glucose
- bilirubin
- aspartate aminotransferase (AST)
- alanine aminotransferase (ALT)

- sodium
- potassium
- corrected calcium
- phosphate
- creatinine clearance

Blood samples for serum hematology are taken at the screening visit, on Days 1, 8, 15, and 22 of Cycles 1-2, Days 1 and 15 of Cycles 3-6, Day 1 of Cycles 7+, and at the End-of-Treatment visit. Blood sample for biochemistry are taken at the screening visit, on Day 1 of each treatment cycle and at the End-of-Treatment visit.

Descriptive statistics (mean, standard deviation, median, range) will be used to summarize observed laboratory values and change from baseline in observed value at each scheduled visit for each treatment group. Line plot of mean with standard error for each laboratory analyte over time will be displayed by treatment group for hemoglobin, neutrophils, lymphocytes, platelets, WBC, AST, ALT, creatinine, and creatinine clearance.

The worst toxicity grade in hematology and chemistry during the treatment will be summarized by treatment group and toxicity grade. Shift tables from baseline to worst toxicity grade during the treatment will be provided for each laboratory analyte listed above. These tables will summarize the number of subjects with each baseline CTC grade and changes to the maximum CTC grade.

5.5. Vital Signs and Physical Examination Findings

Vital signs (systolic and diastolic blood pressure, heart rate, and temperature) values at baseline will be summarized.

Post baseline physical examination findings were collected as AEs, and therefore will not be summarized.

5.6. Electrocardiogram (ECG)

Electrocardiograms (ECG) will be performed at Screening, Day 1 of Cycle 3 and Cycle 6 immediately after end of daratumumab infusion, and End-of-Treatment visit.

The number and percentage of subjects with normal or abnormal 12-lead ECG results will be summarized.

5.7. ECOG Performance Score

ECOG performance status, which evaluates the effect of the disease status on the activities of daily living, will be assessed at Screening, Day 1 of Cycle 3, Cycle 6, Cycle 9 and Cycle 12 for the first year, every 6th cycle thereafter until EOT (PD), post-PD collected at Week 8 and 16. Descriptive statistics will be used to summarize ECOG performance status at baseline, Day 1 of each treatment cycle (including change from baseline), worst score during treatment (including

change from baseline), and End-of-Treatment visit (including change from baseline) for each treatment group. Shift table from baseline to worst score during the treatment will be provided.

6. PHARMACOKINETICS/IMMUNOGENICITY/PHARMACODYNAMICS

Unless specified otherwise, descriptive statistics (e.g., number of observations, mean, standard deviation, median, and range) will be used to summarize pharmacokinetics and pharmacodynamics data. In addition, coefficient variation and geometric mean will be provided in the pharmacokinetic concentration summary.

6.1. Pharmacokinetics

6.1.1. Sampling Timepoints

For subjects assigned to DRd, blood samples to assess serum concentration (pharmacokinetics) of daratumumab will be obtained at Day 1 of Cycle 1, 6 and 12, End-of-Treatment and Post-Treatment Week 8. On a daratumumab dosing day, blood samples need to be collected before (up to 2 hours but not after the start of infusion) and after (up to 2 hours but not before the end of infusion) daratumumab administration.

6.1.2. Pharmacokinetic Parameters

The pharmacokinetic parameters are defined as:

- Minimum observed concentration (C_{min}) the concentration observed immediately before infusion.
- Maximum observed concentration (C_{max}) the concentration observed after the end of infusion

For daratumumab, the pharmacokinetic evaluations include C_{min} and C_{max}.

6.1.3. Analysis Methods

Pharmacokinetic analyses will be performed on the pharmacokinetic-evaluable population. All serum concentrations below the lowest quantifiable concentration or missing data will be recorded as such in the concentration data set. Concentrations below the lowest quantifiable concentration will be treated as zero in the summary statistics. All subjects and samples excluded from the analysis will be clearly documented.

Descriptive statistics will be used to summarize daratumumab serum concentrations at each sampling time point. A plot of mean (±SD) daratumumab serum peak and trough concentrations over time will be provided.

If sufficient data are available, population pharmacokinetic analysis of serum concentration-time data of daratumumab may be performed using nonlinear mixed-effects modeling. If population pharmacokinetic analysis is conducted, it may include data from other clinical studies; details will be provided in a population pharmacokinetic analysis plan and results will be presented in a separate report.

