4.2. Exclusion Criteria

Any potential subject who meets any of the following criteria will be excluded from participating in the study.

- 1. Subject has a diagnosis of primary amyloidosis, monoclonal gammopathy of undetermined significance, or smoldering multiple myeloma. Monoclonal gammopathy of undetermined significance is defined by presence of serum M-protein <3 g/dL; absence of lytic bone lesions, anemia, hypercalcemia, and renal insufficiency related to the M-protein; and (if determined) proportion of plasma cells in the bone marrow of 10% or less (Kyle 2003). Smoldering multiple myeloma is defined as asymptomatic multiple myeloma with absence of related organ or tissue impairment end organ damage (Kyle 2003, Kyle 2007). 17,19
- Subject has a diagnosis of Waldenström's disease, or other conditions in which IgM
 M-protein is present in the absence of a clonal plasma cell infiltration with lytic bone
 lesions.
- 3. Subject has prior or current systemic therapy or SCT for multiple myeloma, with the exception of an emergency use of a short course (equivalent of dexamethasone 40 mg/day for 4 days) of corticosteroids before treatment.
- 4. Subject has a history of malignancy (other than multiple myeloma) within 5 years before the date of randomization (exceptions are squamous and basal cell carcinomas of the skin and carcinoma in situ of the cervix, or malignancy that in the opinion of the investigator, with concurrence with the sponsor's medical monitor, is considered cured with minimal risk of recurrence within 5 years).
- 5. Subject has had radiation therapy within 14 days of randomization.
- 6. Subject has had plasmapheresis within 28 days of randomization.
- 7. Subject is exhibiting clinical signs of meningeal involvement of multiple myeloma.

- 8. Criterion modified as per Amendment INT-2
 - 8.1a) Subject has known chronic obstructive pulmonary disease (COPD) with a Forced Expiratory Volume in 1 second (FEV1) <50% of predicted normal. Note that FEV1 testing is required for subjects suspected of having COPD and subjects must be excluded if FEV1 <50% of predicted normal.
 - 8.1b) Subject has had known moderate or severe persistent asthma within the last 2 years (see Attachment 7), or currently has uncontrolled asthma of any classification. (Note that subjects who currently have controlled intermittent asthma or controlled mild persistent asthma are allowed in the study).
- 9. Criterion modified as per Amendment INT-2

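### The SAP sets daratumumab concentrations below quantification to zero but also plans a geometric mean, which a single zero makes 0 or undefined

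*SAP*

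**What the plan says.** The conflict lies between two parts of the SAP.

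- SAP 6, opening paragraph, lists the usual descriptive statistics (number of observations, mean, SD, median, range) and then adds: "In addition, coefficient variation and geometric mean will be provided in the pharmacokinetic concentration summary".
- SAP 6.1.3 gives the rule for low values: "Concentrations below the lowest quantifiable concentration will be treated as zero in the summary statistics". It also sets the level of the table: "Descriptive statistics will be used to summarize daratumumab serum concentrations at each sampling time point".
- SAP 6.1.1 gives the schedule. Samples "will be obtained at Day 1 of Cycle 1, 6 and 12, End-of-Treatment and Post-Treatment Week 8", and on a dosing day "blood samples need to be collected before (up to 2 hours but not after the start of infusion) and after" daratumumab is given. Cycle 1 Day 1 therefore has a sample drawn before any exposure.

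Nothing exempts the geometric mean from the zero rule, gives it a substitution or exclusion rule of its own, or says that it is left blank when zeros occur. The remark in SAP 6.1.3 about excluded subjects and samples only asks that exclusions be documented. Protocol 11.4 carries the same zero rule but plans no geometric mean.

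**The concern.** The zero rule suits every statistic in the table except the geometric mean. A mean, SD, median and range all accept zeros; a geometric mean does not. A programmer who follows the SAP to the letter would print 0, or an error, at any time with even one value below quantification. A programmer whose software skips zeros without notice would print a figure for the measurable samples only, beside an arithmetic mean that includes the zeros, with nothing to show that the two have different denominators. Two people following the same SAP could thus produce different tables.

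Pharmacokinetics is a stated secondary objective with few sampling times, so each row of the table carries some weight. What is at stake is the readability and reproducibility of that descriptive table.

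**Working it through.** **Inputs from the documents.** The zero rule and the by-time summary (SAP 6.1.3), the planned geometric mean (SAP 6), and the sampling times (SAP 6.1.1). There is no figure in the plan to reproduce.

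**Step 1: the algebra.** For n values x₁ … xₙ,

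GM = (x₁ × x₂ × … × xₙ)^(1/n) = exp[(1/n) Σ ln xᵢ].

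If one xᵢ is 0, the product is 0 and so is its n-th root. In the logarithmic form ln(0) does not exist; software returns either minus infinity, which leads to 0, or an error. The size of the other n − 1 values makes no difference. This step needs no assumption.

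**Step 2: where zeros can arise.**

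- *Cycle 1 Day 1 before infusion.* No daratumumab has been given. Protocol 4.2 also bars earlier myeloma treatment: "Subject has prior or current systemic therapy or SCT for multiple myeloma, with the exception of an emergency use of a short course" of corticosteroids. Values below quantification are to be expected in practically everyone. The geometric mean is then 0 or undefined. If every value is zero, the arithmetic mean is 0 too and a coefficient of variation of SD/mean is 0/0.
- *End-of-Treatment and Post-Treatment Week 8.* These follow the end of dosing. Protocol 6.4 lets a subject stop daratumumab and stay on the other drugs, and Protocol 9.1.3 ties the End-of-Treatment visit to the last dose of all study treatments, so some of these samples may be taken well after the last daratumumab dose. Low values are possible, but the documents give no quantification limit, half-life or expected count.

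**Step 3: illustration.** Assumed, and not in the documents: 300 lognormal values, true geometric mean 500, coefficient of variation 60%, quantification limit 0.2 in the same units, and k of the values replaced by zero. A separate sample was drawn for each k.

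| k of 300 | Arithmetic mean, zeros included | GM as the SAP is written | GM, quantifiable only | GM, half the limit (0.1) substituted |
|---|---|---|---|---|
| 1 | 579.3 | 0 | 504.7 | 490.6 |
| 30 | 512.4 | 0 | 487.8 | 208.7 |
| 300 | 0 | 0 | not calculable | 0.1 |

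The SD of the logarithms could not be computed in any of these rows.

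**Step 4: why the choice of repair matters.** If k values are replaced by a constant c,

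GM = exp{[(n − k) ln GM₊ + k ln c] / n},

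where GM₊ is the geometric mean of the quantifiable values. For k = 30 and c = 0.1:

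0.9 × ln(487.85) + 0.1 × ln(0.1) = 5.571 − 0.230 = 5.341, and exp(5.341) ≈ 208.7.

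Substituting half the limit in 10% of samples lowers the figure by 1 − 208.7/487.8 = 57%. With c = 0.2 (the full limit) the result is 223.7. The answer is driven by an arbitrary constant.

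**The case against.** The strongest reply is that this is a table-programming detail. The geometric mean is an extra statistic beside several that accept zeros; the planned plot uses mean ± SD; population modelling, if done, has its own plan and report; and no test uses the geometric mean. Nothing is lost from the data either: "All serum concentrations below the lowest quantifiable concentration or missing data will be recorded as such in the concentration data set", so a table can be corrected at any time. All of this stands, and it caps the importance of the point. It does not remove it, because here a stated rule gives a wrong result; it is not merely silent.

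The one certain case is also harmless. A geometric mean of 0 or a blank before the first dose misleads nobody. That stands too.

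A reader might go further in three ways that the documents do not support.

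- *That values below quantification are to be expected at Post-Treatment Week 8.* Without a quantification limit or half-life, this cannot be said. Protocol 9.8 reports that interference with the indirect antiglobulin test can last up to 6 months after treatment, which, if anything, suggests that drug persists. It does not prove that Week 8 values are quantifiable.
- *That dropping zeros overstates the geometric mean by a known amount.* With a lognormal of median 300 and log-SD 0.8, cutting off the lowest 0.5%, 5% or 20% of 200 values raises it by about 1%, 9% or 33%. But the 5% and 20% cases put the quantification limit at 300 × exp(−1.645 × 0.8) ≈ 80 and 300 × exp(−0.842 × 0.8) ≈ 153, a quarter to a half of the median, which nothing in the documents supports. In the illustration above, where zeros are not simply the low tail, leaving them out gave 487.8 against a true 500, so no inflation.
- *That the protocol has the same fault.* Protocol 11.1 and 11.4 plan no geometric mean, so their zero rule is workable as it stands.

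**Conclusion.** The point holds in a limited form. SAP 6 and SAP 6.1.3, read together, yield a geometric mean that is 0 or undefined at any sampling time with at least one value below quantification. That conclusion is pure arithmetic and rests on no assumption about the data. Its occurrence is certain only at the first predose sample. At the two post-dosing times it is conditional on at least one such value, and no frequency or size of distortion can be given from the documents; the illustrative numbers rest on assumed inputs. The consequence is confined to descriptive pharmacokinetic tables. No efficacy or safety conclusion and no significance level is touched, and the priority is low.

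**What to change.** Replace the single zero rule in SAP 6.1.3 with text along these lines:

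> For n, arithmetic mean, SD, median and range, a value below the quantification limit enters as zero. The geometric mean is calculated from quantifiable values only, its own n is displayed, and it is left blank where no value is quantifiable. The number and percentage of values below the limit are displayed for every sampling time.

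The same edit should say which coefficient of variation is meant. An arithmetic one follows the zero rule and is blank where the mean is 0; a geometric one follows the geometric mean.

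A substitution such as half the limit is not recommended as the default, because of the sensitivity shown in Step 4.

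The cost is a few lines in the SAP and some extra table columns, with no new data. The drawback is that the geometric mean will rest on fewer subjects than the arithmetic mean in the same row and will describe only those with measurable drug. Showing both denominators and the percentage below quantification lets the reader see this.
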